## LIST OF ABBREVIATIONS

AE	Adverse event
ALP	Alkaline phosphatase
ALT	Alanine aminotransferase
ANC	Absolute neutrophil count
AST	Aspartate aminotransferase
BUN	Blood urea nitrogen
CBC	Complete blood cell (count)
CHO	Community Hematology & Oncology
CFR	United States Code of Federal Regulations
CP	Child-Pugh criteria
CR	Complete response
CRMS	Clinical research management system
CRQA	Clinical Research Quality & Administration
CRRC	Clinical Research Review Committee (OHSU)
CRF	Case report form
CSF	Cerebral spinal fluid
CT	Computerized tomography
CTEP	Cancer Therapy Evaluation Program
CTCAE	Common Terminology Criteria for Adverse Events
CTMS	Clinical Trial Management System
DFS	Disease-free survival
DLT	Dose limiting toxicity
DSMC	Data and Safety Monitoring Committee
DSMP	Data and Safety Monitoring Plan
ECG	Electrocardiogram
ECOG	Eastern Cooperative Oncology Group
eCRF	Electronic Case Report Form
eCRIS	Electronic Clinical Research Information System
EDC	Electronic data capture
FDA	United States Food and Drug Administration
GCP	Good Clinical Practice
HBeAg	Hepatitis B "e" antigen
HBV	Hepatitis B virus
HCC	Hepatocellular carcinoma
HCT	Hematocrit
HCV	Hepatitis C virus
HGB	Hemoglobin
HIPAA	Health Insurance Portability and Accountability Act
HIV	Human immunodeficiency virus
ICH	International Conference on Harmonization
IRB	Institutional Review Board
LDH	Lactate dehydrogenase
LDT	Liver directed therapy
LFT	Liver function test
LTX	Liver transplantation
MRI	Magnetic resonance imaging
MTD	Maximum tolerated dose
N/A	Not applicable
NCI	National Cancer Institute
OHRP	Office for Human Research Protections

OHSU	Oregon Health & Science University
PD	Progressive Disease
PET	Positron emission tomography
PI	Principle Investigator
PR	Partial response
QOL	Quality of Life
RBC	Red blood cell (count)
RILD	Radiation-induced liver disease
RNI	Reportable new information
RT	Radiation therapy
SAE	Serious adverse event
SBRT	Stereotactic body radiotherapy
SD	Stable disease
SD	Standard deviation
TAE/TACE	Transarterial embolization / transarterial chemoembolization
TSMP	Trial Specific Monitoring Plan
ULN	Upper limit of normal
UP	Unanticipated problem
WBC	White blood cell (count)

## 1. BACKGROUND INFORMATION AND SCIENTIFIC RATIONALE

### 1.1 OVERVIEW OF HEPATOCELLULAR CARCINOMA

Hepatocellular carcinoma (HCC) accounts for 90% of liver cancers worldwide, with an approximately 782,000 new cases and 746,000 deaths expected in 2012. In the United States alone, HCC is attributed to nearly 30,000 deaths annually. The age-adjusted worldwide incidence of HCC is 10.1 cases per 100 000 person-years, and this number is expected to continue rising as the number of hepatitis C virus (HCV) carriers increases.

Partial hepatectomy or LTX are the only available curative treatments; however, >80% of patients with HCC have chronic liver disease, and mandatory hepatic reserve requirements often exclude many patients with advanced cirrhosis from liver resection. In patients with early to intermediate-stage HCC and advanced liver disease, LTX confers superior disease-free survival compared to resection. Whether a patient is eligible for LTX is largely based on the Milan selection criteria established by Mazzaferro et al, which demonstrated that LTX recipients with early HCC (as defined by having either a single lesion no > 5 cm or ≤ 3 lesions each ≤ 3 cm) can achieve favorable long term patient survival. Unfortunately, prolonged wait times pose a major disadvantage to patients awaiting suitable livers. Rather, using these criteria, 20-30% of listed patients will have oncologic progression outside of the Milan criteria during this waiting period. To minimize the risks of disease progression, a bridge-to-LTX using LDT is often recommended. Whereas ideal candidates for LDT have preserved liver functions with Child-Turcotte-Pugh (CP) scores of B7 or better, many LTX candidates with advanced cirrhosis (CP-B8 or higher) are excluded from treatment as they lack sufficient hepatic reserve.

### 1.2 LIVER DIRECTED THERAPIES

Alternative therapeutic approaches to LTX for patients with unresectable HCC include, partial hepatectomy, radiofrequency ablation, transarterial embolization/chemoembolization (TAE/TACE), and radioembolization, among others. Unfortunately, many of these approaches are associated with procedural complications that can cause significant morbidity.

TACE with the transcatheter delivery of a mixture of chemotherapy and embolic agents is considered standard of care for early and intermediate stage unresectable HCC patients with preserved liver function. This approach is associated with a strong response rate (OR: 5.95; 95%CI: 2.96–11.99), and is significant survival benefit over best supportive therapy (HR: 0.76; 95%CI: 0.64–0.91). However, major complications associated with this approach include (but are not limit to): hepatic failure, liver abscess, liver rupture, biliary tract injury, renal failure, necrotizing pancreatitis, cerebral lipiodol embolism, and hepatic encephalopathy. Aside from complications, use of TACE is also limited by cases of excessive tumor burden (i.e., <50% of liver) and minimum tumor size (i.e., >5 cm) requirements, as well as limitations of vascular invasion, biliary obstruction, and anatomical localization (e.g., infradiaphragmatic or adjacent to large vessels). Moreover, TACE, is generally not performed for patients having Child-Pugh classification C (or late B); further highlighting the limited treatment option for patients with severely compromised liver function.

#### 1.2.1 STEREOTACTIC BODY RADIOTHERAPY OF LIVER IN SETTING OF ADVANCED CIRRHOSIS

Guidelines have historically omitted external beam radiation therapy for the management of HCC because of the high incidence of radiation-induced liver disease (RILD). Modern advances to computer and imaging technologies have greatly improved methods of conformal

liver irradiation, which are associated with RILD  $\leq$  5%. SBRT involves the use of a few ( $\leq$ 10) potent doses of highly conformal radiation therapy with high geometric precision and accuracy. These advances have renewed interest in SBRT as an approach to managing HCC, with data from several studies supporting its safety and efficacy in patients with the greatest degree of hepatic reserve.

Bujold et al reported on the outcomes of a prospective trials consisting of 102 evaluable patients with HCC (CP-A) that were treated with SBRT. The underlying liver disease among patients consisted of hepatitis B (38%), hepatitis C (38%), alcohol related (25%), other disease (14%), and no disease (7%). The authors evaluated patients 1-year after receiving SBRT (dose range: 24 to 54 Gy in six fractions), and observed local control of 87%, and a median overall survival of 17 months. Toxicity  $\geq$  grade 3 was reported in 30% of patients. Importantly, no RILD was observed.

Lasley et al conducted a phase 1-2 trial to examine variables influencing liver toxicity in patients receiving SBRT for hepatocellular carcinoma. In this study, 38 CP-A (39 lesions) and 21 CP-B (26 lesions) patients were followed for  $\geq$ 6 months following SBRT. The authors observed that local control at 6 months was 92% for CP-A and 93% for CP-B. Two- and 3-year estimates with local control was 91% for CP-A and 82% for CP-B ( $P = .61$ ). The median overall survival was 44.8 months and 17.0 months for CP-A and CP-B. Assessment of safety among CP-A and CP-B patients revealed 4 (11%) and 8 (38%) patients that experienced grade III/IV liver toxicity, respectively. The authors further reported that the risk of death was 4.6 times greater for CP-A patients with  $\geq$ grade III liver toxicity compared to those without toxicity. In contrast, no such correlation was seen for CP-B patients. Notably, CP-B patients experiencing grade III/IV liver toxicity had significantly higher mean liver dose, higher dose to one-third normal liver, and larger volumes of liver receiving doses  $<2.5$  to 15 Gy in 2.5-Gy increments. This finding suggests that for CP-B patients, careful consideration should be given to low-dose volumes that could potentially result in increased liver toxicity. Overall, the authors concluded that SBRT is safe for therapy of patients with HCC.

In a recent retrospective study, Nabavizadeh et al reported on their single institution experience using SBRT or hypofractionated radiation therapy (AHRT) to treat 146 HCC patients with varying degrees of cirrhosis. The cohort included 51 patients with CP-B8 or higher cirrhosis (34% of entire cohort). Within this cohort, only a third of all patients experienced toxicity, defined as a CP elevation of 2 or more within 6 months of RT. These findings are comparable with other reports. Notably, the authors did not identify a statistically significant difference between rates of toxicity when comparing patients with CP-B8 or higher baseline cirrhosis to those with CP-A or B7 cirrhosis. Thirteen patients in the cohort with CP-B8 or higher cirrhosis eventually underwent LTX; suggesting that radiotherapy affords localized disease control for these patients awaiting transplantation. In this regard, the authors further observed that the 1- and 2-year local control (LC) rates were greater significantly better among patients receiving SBRT compared to those given AHRT (1-year LC 97% vs 72%,  $P <.0001$ ; 2-year LC 94% vs 65%,  $P <.0001$ ).

### 1.3 RATIONALE

Liver transplantation (LTx) is the best treatment for patients with hepatocellular carcinoma HCC and CP-B or C cirrhosis, as both conditions can be very effectively treated at once. As LTx wait-lists can be many months, LDTs are essential as oncologic temporizing measures to bridge patients to LTx. However, due to the fear of further hepatic decompensation, many patients with advanced cirrhosis are excluded from receiving LDT. Rather, recent studies suggest that SBRT can be of safe and practical use in this fragile patient population, and thereby reduce the rate of transplantation drop-out.

In this pilot study of HCC patients with severe cirrhosis, the feasibility of utilizing SBRT will be evaluated as a stopgap method to provide localized disease control until time of transplantation. By achieving the study endpoints listed in Section 3.2, this pilot trial will contribute to the development of a larger-scaled multi-institutional clinical trial of SBRT in HCC patients with advanced hepatic decompensation by sharpening our hypothesis, identifying barriers to subsequent study participation and estimating bridging efficacy relative to historical controls.

## 1.4 POTENTIAL RISKS AND BENEFITS

#### 1.4.1 KNOWN POTENTIAL RISKS

The use of SBRT is associated with increased risk for radiation-induced liver disease and further decompensation of liver function. At Oregon Health and Science University, the treatment of patient with severely compromised liver function is associated with a 31% increase in liver toxicity, as determined by an increase CP score of  $\geq 2$  within 6 months after SBRT. Only 11 of 146 patients (7.5%) were observed to have a Grade 4 toxicities (per Common Terminology Criteria for Adverse Event [CTCAE] criteria) within 6 months of RT. These grade 4 AEs consisted of 1 gall bladder perforation, 4 cases of thrombocytopenia, 2 cases of hyperbilirubinemia, 2 cases of upper gastrointestinal bleeding, and 2 cases of encephalopathy; however, no definitive treatment-related deaths were seen. In comparison, authors of a separate institutional study observed that 26% of 101 patients with baseline CP-A cirrhosis and 7 of 13 (53%) of patients with CP-B7 cirrhosis experienced CP  $\geq 2$  toxicity within 3 months of 6-fraction SBRT. However, it is very challenging to discern treatment-related hepatic toxicity from natural decline of hepatic functionality secondary to advanced cirrhosis. For example, the SHARP trial, a randomization of placebo versus sorafenib for advanced HCC, identified that the placebo arm had a 52% rate of adverse events likely due to cirrhosis or HCC progression. Refer to Section 8.4 for additional information.

#### 1.4.2 KNOWN POTENTIAL BENEFITS

There are a minimal number of approaches currently available to help bridge the time to transplantation in patients with severely compromised liver function. The current study using SBRT may provide access to a new treatment approach not previously available. It cannot, however, be guaranteed that participants in this study will directly benefit from treatment during participation, as the clinical trial is designed to provide information about the safety and effectiveness of the investigational approach.

## 2. OBJECTIVES

## 2.1 PRIMARY OBJECTIVES

Assess the use of SBRT in HCC patients with advanced liver cirrhosis as a feasible approach to providing localized disease control that adequately suffices liver transplant eligibility criteria.

## 2.2 SECONDARY OBJECTIVES

Assess preliminary efficacy and toxicity in HCC patients with advanced cirrhosis following liver SBRT.

## 2.3 EXPLORATORY OBJECTIVES

Assess quality of life in HCC patients with advanced cirrhosis following liver SBRT. Examine SBRT-related histopathologic changes in explanted livers of patients with advanced cirrhosis.

### 3. STUDY DESIGN AND ENDPOINTS

#### 3.1 DESCRIPTION OF THE STUDY DESIGN

*Refer to Section 9, Statistical Considerations, for additional information regarding statistical methods used in this study.*

This is pilot study to assess the feasibility of bridge-to-transplantation SBRT for patients with severe liver disease. Participants must meet the inclusion criteria, have none of the exclusion criteria, and have provided written informed consent before the conduct of any screening tests not performed routinely in their treatment.

In general, patients with CP-B8 or higher cirrhosis and non-metastatic HCC who have been listed or recommended to be listed for liver transplantation will be eligible for participation in this study. Eligible participants will undergo SBRT consisting of 40 Gy to be given in 5 fractions every other day provided that criteria for normal organ constraints are met (i.e.,  $\geq 700$  cc of uninvolved liver). In cases where normal organ constraints are not met, the dose will be iteratively de-escalated to two dose levels (35 Gy in 5 fractions, then 30 Gy in 5 fractions). If normal organ constraints are unable to be met at 30 Gy in 5 fractions, the participant will be considered ineligible for SBRT and considered a screen failure.

Following SBRT, the rate of radiation-induced liver disease (non-classical RILD) and associated toxicities will be evaluated, along with treatment response and an assessment of quality of life associated with SBRT. The proportion of participants that are successfully bridged to liver transplantation, and times to liver transplantation following SBRT will be recorded for each participant. Additional exploratory studies will assess SBRT-related histopathologic changes in explanted livers of participants with advanced cirrhosis. In these studies, pathologic treatment response in explanted livers will be evaluated, and regions of uninvolved liver both near and remote to the irradiated volume will be assessed for histopathologic changes consistent with RILD (e.g., obliteration of central veins, increased perisinusoidal reticulin network and hepatocyte necrosis).

This study aims to enroll 15 participants at OHSU. Participant data for primary, secondary, and exploratory endpoints will be collected by the site providing clinical care. The analyses of the data collected will take place at OHSU.

#### 3.2 STUDY ENDPOINTS

##### 3.2.1 PRIMARY ENDPOINT

Endpoint	Start	End
Proportion of participants who are transplanted or with localized disease control that meets Milan criteria (Section 7.5) within 1 year	Start of SBRT	Time of progression, or transplantation, or 1-years after last SBRT dose, whichever occurs first

##### 3.2.2 SECONDARY ENDPOINTS

Endpoint	Start	End
1. Localized control rate: Incidence of progressive disease within or at the planned tumor volume (PTV) margin		Time of progression, transplantation, death or 2-years after last SBRT dose, whichever occurs first.
2. Incidence of intrahepatic progressive disease		
3. Incidence of extrahepatic progressive disease		
4. Proportion of participants that proceed to transplantation	First dose of SBRT	
5. Overall Survival		Time of death or 2-years after last SBRT dose
6. Incidence of non-classic RILD, defined as grade 4 aspartate aminotransferase or alanine aminotransferase elevation, or an increase in CP score of $\geq 2$ within 1 week to 3 months after completing SBRT (Appendix A)		3 months after last SBRT dose

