## 7.3 EFFICACY CRITERIA FOR TUMOR RESPONSE

### 7.3.1 EVALUATION OF TARGET LESION

**Progressive Disease (PD):** An increase of at least 20% in the sum of the diameters of viable (enhancing) target lesions, taking as reference the smallest sum of the diameters of viable (enhancing) target lesions recorded since treatment started

**Non-Progressive Disease** Any cases that do not qualify for progressive disease

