#### 7.3.2.1 *Evaluation of New Lesions*

A new liver nodule is classified as HCC, and will therefore be declared as a progression, when its longest diameter is  $\geq 10$  mm and it presents the typical enhancement of HCC on dynamic imaging, i.e. contrast uptake during the arterial phase with portal vein/delayed phase washout. Liver lesions  $\geq 10$  mm, which do not exhibit typical enhancement dynamics may be diagnosed as HCC if they increase of  $\geq 10$  mm on subsequent scans. In this latter case, the date of progression used a posteriori will be the date of first detection of the lesion.

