## 7.5 MILAN CRITERIA

Participant eligibility for transplantation will be based on guidelines reported by Mazzaferro et al. To be considered eligible for liver transplantation, participants with HCC must have disease as follows:

- Single tumor with diameter  $\leq 5$  cm **OR** up to 3 tumors, each with diameter  $\leq 3$  cm, **AND**
- No major vessel or extra-hepatic involvement.

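### As laid out in 3.2.2, the window for the proportion transplanted closes at progression, which can occur within Milan, and other sections set no such limit

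*Combined protocol and SAP*

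**What the plan says.** **Window.** The table in 3.2.2 lists "4. Proportion of participants that proceed to transplantation" among the secondary endpoints. The end of observation shown for the block of endpoints 1 to 4 is "Time of progression, transplantation, death or 2-years after last SBRT dose, whichever occurs first". Overall survival has a separate end, "Time of death or 2-years after last SBRT dose", which does not stop at progression, and non-classic RILD has its own 3-month end.

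**Progression.** For target lesions, 7.3.1 defines it as "An increase of at least 20% in the sum of the diameters of viable (enhancing) target lesions", measured from the smallest sum since treatment started, with no absolute minimum. For new lesions, 7.3.2.1 says: "A new liver nodule is classified as HCC, and will therefore be declared as a progression, when its longest diameter is" at least 10 mm with typical enhancement. Neither rule refers to Milan.

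**Eligibility.** Section 7.5 allows a single tumor up to 5 cm, or "up to 3 tumors, each with diameter" of 3 cm or less, without major vessel or extrahepatic involvement. Section 1.1 gives the same size and number limits: "having either a single lesion no > 5 cm or ≤ 3 lesions each ≤ 3 cm".

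**Follow-up and analysis.** The Synopsis ends follow-up at the first of progression, transplantation or 2 years. Section 4.7 lists progression among the criteria that can take a participant off study. Section 6.5 instead continues to hospice enrollment, death or 2 years. Section 3.1 says: "The proportion of participants that are successfully bridged to liver transplantation, and times to liver transplantation following SBRT will be recorded for each participant". Section 9.2.3 reports the transplant proportion in the efficacy set with a 95% CI and gives neither a window nor a rule for a transplant after progression.

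**The concern.** Stopping at progression suits endpoints 1 to 3, where progression is the event. For endpoint 4 the event is transplantation. If progression closes the window, the quantity becomes the proportion transplanted with no earlier progression, which is a different quantity from the proportion transplanted.

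The difference matters because Section 1.3 says the pilot will inform a larger trial by comparing bridging efficacy with historical controls. The institutional cohort in 1.2.1 (13 of 51 patients with CP-B8 or higher eventually transplanted) is described without a progression cut-off. A proportion that stops at progression would not be on the same footing.

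There is also a mismatch inside the plan. Explant histopathology (3.2.3) is assessed at transplantation with no progression limit, so a participant could contribute an explant yet fall outside the transplant count.

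**Working it through.** **1. The plan's own figure.** The plan states no expected transplant proportion. Its one design calculation is the sample size in 9.3.1: ln(1 − 0.95)/ln(1 − 0.20) = 13.43, rounded up to 14, against 15 planned. With 15 patients the chance of at least one SBRT-ineligible patient is 1 − 0.80^15 = 0.965. This does not depend on endpoint 4.

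**2. Can progression occur inside Milan?** Inputs are the 20% rule (7.3.1), the 10 mm rule (7.3.2.1) and the limits in 7.5. Assume no major vessel or extrahepatic disease, and take viable diameter as tumor diameter.

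- Single lesion with smallest diameter d: growth of 20% stays within 5 cm if 1.2 × d ≤ 5, so d ≤ 5/1.2 = 4.17 cm. For example, 2.0 cm growing to 2.4 cm is progression and inside Milan.
- Two or three lesions: each stays within 3 cm after 20% growth if d ≤ 3/1.2 = 2.5 cm.
- New nodule: one or two lesions of up to 3 cm plus one new 1.0 cm nodule make two or three lesions, each within 3 cm.

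**3. A constructed case.** A 2.5 cm lesion is irradiated, a typical new 1.2 cm nodule appears at month 6, and the patient is transplanted at month 9. Month 6 is progression. The patient then has two tumors of 3 cm or less and is inside Milan.

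| Section | Treatment of the month-9 transplant |
|---|---|
| 3.2.2, End read as shared | After the window has closed |
| Synopsis follow-up | After follow-up has ended |
| 4.7 | Participant may already be off study |
| 6.5 | Still in follow-up |
| 3.1 and 9.2.3 | No progression limit stated |

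**4. Size per participant.** With all 15 in the efficacy set, each transplant left out costs 1/15 = 6.7 percentage points. Fewer than 15 in that set (9.1 requires 85% of the prescribed dose) makes each one cost more. The cut-off removes transplants and never adds any, so it acts in one direction.

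**5. Illustration only.** Scaling the cohort in 1.2.1 gives 15 × 13/51 = 3.8, about 4 transplants.

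| Transplants counted | Proportion | Exact 95% CI |
|---|---|---|
| 4 of 15 | 26.7% | 7.8 to 55.1% |
| 3 of 15 | 20.0% | 4.3 to 48.1% |
| 2 of 15 | 13.3% | 1.7 to 40.5% |

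The share q of transplants that follow progression is not in the documents. Assuming q from 10% to 40%, the expected reported proportion, 4 × (1 − q)/15, runs from 24.0% down to 16.0%. The chance that at least one of the four is left out, 1 − (1 − q)^4, runs from 34% to 87%.

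**The case against.** A reader might infer that the plan scores every patient transplanted after progression as not transplanted. The documents do not go that far, for three reasons.

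- **The shared End is an inference.** In the text as extracted from the PDF, the End wording sits on the row for endpoint 1 and the End cell for endpoint 4 is blank. A merged cell is the natural reading: overall survival and RILD have their own ends, and the wording lists transplantation. If it does not cover endpoint 4, that endpoint has no stated end, which also needs correcting.
- **Other sections would let the transplant be counted.** Section 6.5 keeps the patient in follow-up, and 3.1 and 9.2.3 set no progression limit. Nor does 3.2.2 say which progression (local, intrahepatic or any) would close the window. The list could be read as applying each event only where relevant. The fair description is a conflict between sections.
- **Transplantation without prior progression is a coherent measure.** Section 1.3 frames bridging as local disease control until transplantation, and the primary endpoint's window in 3.2.1 also ends at progression. This stands as an argument for reporting that quantity. It does not justify leaving the choice unstated, and reporting both quantities answers it.

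The objection to the illustration also stands. The cohort was retrospective, mixed SBRT with hypofractionated radiotherapy, and had no 2-year transplant window. Its 1-year local control of 97% with SBRT suggests that regrowth in the treated lesion may be uncommon, although that figure does not address new nodules elsewhere in the liver. The confidence intervals overlap heavily, and this is a pilot without a formal test.

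**Conclusion.** The point holds as a conflict over the window for endpoint 4. With the End in 3.2.2 read as shared, observation for the transplant proportion stops at progression, and progression as defined can occur within Milan. The Synopsis and 4.7 lean the same way; 6.5, 3.1 and 9.2.3 do not. Two analysts following the plan could report different proportions from the same data.

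The direction is certain if the table is followed literally: the proportion can only fall, by 6.7 points per affected participant with all 15 in the efficacy set. The total effect is unknown, because the documents give no rate of within-Milan progression followed by transplantation. The falls from 26.7% to 20.0% or 13.3% rest on an assumed four transplants and an assumed one or two left out. They should not be read as an estimate of bias.

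It would be wrong to conclude that such transplants are excluded throughout the plan. The sample size is unaffected. The matter should be settled before analysis because this secondary endpoint lies so close to the trial's bridging question.

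**What to change.** 1. In 3.2.2, give endpoint 4 its own end: transplantation, death or 2 years after the last SBRT dose, whichever is first. State that progression does not end the window.
2. In 9.2.3, report the proportion transplanted by 2 years, split by whether progression occurred before transplant. This also preserves the progression-free version for anyone who prefers it.
3. Align the Synopsis follow-up, 4.7 and 6.5 so that transplant status and date are still collected after progression, except where a participant has withdrawn consent.

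The cost is one table entry, a sentence in 9.2.3, matching edits to three follow-up passages, and a chart check of transplant status after progression. Section 4.1 requires participants to be listed or recommended for listing at the participating institution, so the record should usually be at hand. Treatment is unchanged.

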Secondary Endpoints	
 
1. Incidence of progressive disease within or at the planned tumor volume (PTV) margin (i.e. local control)
 
2. Incidence of progressive disease within any section of the liver, including the PTV (e.g. intrahepatic disease free survival)
 
3. Incidence of progressive disease outside of the liver (e.g. extrahepatic disease free survival)
 
4. Overall Survival
 
5. Proportion of participants that proceed to transplantation
 
6. Incidence of non-classical radiation-induced liver disease (RILD), defined as grade 4 aspartate aminotransferase or alanine aminotransferase elevation, or an increase in CP score of <math>\geq 2</math> within 1 week to 3 months after completing SBRT.
 

	7. Incidence of liver toxicity per CTCAE v5.0 within 1 week to 3 months after completing SBRT.
Exploratory Endpoints	
 
1. QoL scores for EORTC QLQ-C30 questionnaire
 
2. QoL scores for Functional Assessment of Cancer Therapy-Hepatobiliary (FACT-Hep) questionnaire
 
3. At time of transplantation, histopathologic changes in irradiated tumor sites relative to uninvolved liver tissue will be assessed
 

Number of Participants	15
Duration of Therapy	SBRT will be administered as 5 fractions every other day (~10 day)
Duration of Follow Up	Time of progression, or transplantation, or 2-years after last SBRT dose, whichever occurs first
Key Inclusion Criteria	
 
1. Participants aged <math>\geq 18</math> years
 
2. Patient diagnosed with HCC and recommended for LTX
 
3. Meets clinical criteria for eligibility for SBRT to the target lesion
 
4. Childs-Pugh Class B8 or higher
 
5. Eastern Clinical Oncology Group performance status <math>\leq 2</math>
 
6. Safe radiation treatment planning parameters that adhere to all organs at risk constraints per section 5.1 of the protocol. If normal organs at risk constraints (including at least 700cc of uninvolved liver) are unable to be met at the lowest dose modification (30 Gy in 5 fractions), the patient is deemed ineligible for SBRT and deemed a screen failure.
 

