## 4.7 OFF-STUDY CRITERIA

Criteria that can take a participant off-study include:

- Participant requests to be withdrawn from study without further follow-up,
- Completed study follow-up period,
- Progression of disease,
- Death,
- Screen failure,
- Investigator's discretion

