### 7.3.3 LOCAL CONTROL RATE

Local control is defined as the absence of progressive disease (per Section 7.3.1) within the PTV or at the PTV margin, measured from time of first SBRT dose to time of progression or transplantation, or 2 years from last SBRT dose, whichever occurs first.

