### 7.3.4 INTRAHEPATIC PROGRESSION-FREE SURVIVAL

Intrahepatic progression-free survival (PFS) is defined as the development of intrahepatic recurrent or new disease within any section of the liver, including the PTV. The consideration of whether a lesion is within or adjacent to the PTV is determined by the individual site investigator. Intrahepatic PFS is measured from time of first SBRT dose to time of progression or transplantation, or 2 years from last SBRT dose, whichever occurs first.

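### The stop event 'progression' names no site for the local, intrahepatic and extrahepatic endpoints and conflicts with 2-year follow-up, so later PTV failure or metastasis may go unobserved

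*Combined protocol and SAP*

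**What the plan says.** **End of the window.** In the section 3.2.2 table the End entry "Time of progression, transplantation, death or 2-years after last SBRT dose, whichever occurs first" stands beside endpoint 1 (local), and the cells for endpoints 2 (intrahepatic), 3 (extrahepatic) and 4 (transplantation) are blank. Endpoint 5 has its own entry. One entry shared by endpoints 1 to 4 is the natural reading, although it rests on a table extracted from PDF.

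**Definitions.** Section 7.3.3 first fixes the local event: "Local control is defined as the absence of progressive disease (per Section 7.3.1) within the PTV or at the PTV margin". It then says that local control is "measured from time of first SBRT dose to time of progression or transplantation, or 2 years from last SBRT dose, whichever occurs first". Section 7.3.4 uses the same stop: "Intrahepatic PFS is measured from time of first SBRT dose to time of progression or transplantation, or 2 years from last SBRT dose". Neither says at which site the stopping progression must lie.

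**What counts as progression.** Section 7.3.2.1 states: "A new liver nodule is classified as HCC, and will therefore be declared as a progression, when its longest diameter is" at least 10 mm and the enhancement is typical. The nodule's position in the liver does not matter.

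**Follow-up.** The synopsis gives the duration of follow-up as "Time of progression, or transplantation, or 2-years after last SBRT dose, whichever occurs first". Section 4.7 includes "Progression of disease" among criteria that can take a participant off study. By contrast, section 6.5 continues disease assessments until hospice, death or 2 years, and section 6.8 (footnotes B and E) continues visits and surveillance imaging for 2 years. Neither stops at progression.

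**Analysis.** Section 9.2.3 plans Kaplan-Meier curves for local control, intrahepatic progression-free survival and overall survival. It names no method for the extrahepatic endpoint and gives no censoring or competing-event rule.

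**The concern.** The three endpoints ask about three different places, but the word that ends observation names none of them. Take a participant with a typical 12 mm nodule in an untreated segment at month 4.5, growth at the PTV at month 10.5 and a metastasis at month 13.5. All three fall on scheduled scans. Read literally, the nodule closes the window at month 4.5, and neither later event counts for endpoint 1 or endpoint 3. Read by site, both count. Two analysts following this plan could report different failure rates from the same scans.

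Local control is what SBRT is meant to deliver, and extrahepatic involvement breaks the Milan criteria in section 7.5. Any loss makes the results look better than they are, and section 1.3 intends them to inform a larger trial. The intrahepatic endpoint is less exposed: an out-of-field nodule is itself its event, so it loses events only after an earlier extrahepatic progression.

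**Working it through.** The plan states no figure on this point, so there is none to reproduce. The size below is an illustration.

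**Inputs**
- Death: the 17.0-month median survival for Child-Pugh B in section 1.2.1 gives a hazard of 12 × ln 2 / 17 = 0.4893 per year, or 39% at 1 year.
- Assumed 1-year risks, with hazard −ln(1 − risk): extrahepatic 10% (0.1054), local failure 5% (0.0513), transplantation 25% (0.2877), out-of-field liver progression 30, 45 or 60% (0.3567, 0.5978, 0.9163).
- The assumed local rate gives 1 − 0.95² = 9.75% failure at 2 years. Section 1.2.1 quotes 2-year local control of 94% and 82%, that is 6% and 18% failure.

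**Formula.** With independent exponential times, the crude 2-year incidence of an event with hazard h is (h/H) × (1 − exp(−2H)), where H is the sum of all hazards that end observation.

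**Extrahepatic, site-specific window.** H = 0.1054 + 0.4893 + 0.2877 = 0.8823 (from unrounded hazards). Incidence = (0.1054/0.8823) × (1 − exp(−1.7646)) = 9.90%, or 1.48 expected events in 15.

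**Extrahepatic, window closed by any progression.** Add the out-of-field and local hazards. At 30%, H = 0.8823 + 0.3567 + 0.0513 = 1.2903, and the incidence is (0.1054/1.2903) × (1 − exp(−2.5806)) = 7.55%.

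| Out-of-field risk at 1 year | Incidence counted | Share of 9.90% lost | Expected events lost in 15 |
|---|---|---|---|
| 30% | 7.55% | 24% | 0.35 |
| 45% | 6.56% | 34% | 0.50 |
| 60% | 5.55% | 44% | 0.65 |

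**Other assumed rates.** With out-of-field progression at 20 to 50% per year, extrahepatic at 5% per year, transplantation or death at 0 to 60% per year and 2-year local failure of 6 to 18%, the share of extrahepatic events lost is 15 to 49%.

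**If sites are correlated.** In a simulation in which the hazard doubles after an out-of-field nodule, 35, 48 and 59% of extrahepatic events are lost. The counted incidence is unchanged, because the window is already closed when the hazard rises. The full incidence is therefore 7.55/0.65 = 11.6%, 6.56/0.52 = 12.6% and 5.55/0.41 = 13.5%, and the loss in 15 participants is 0.61, 0.91 and 1.20 events.

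**Local control.** The same formula takes the crude local incidence from 5.01% to 3.67, 3.19 and 2.70%, a loss of 27, 36 and 46% of events (0.20, 0.27 and 0.35 in 15). That is a loss of counts, not bias in the planned estimate. Kaplan-Meier censors the participant at the nodule. With independent hazards the local hazard before the nodule is still 0.0513, so both windows estimate 1 − exp(−2 × 0.0513) = 9.75%.

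If the local hazard L doubles after a nodule (hazard O), the probability of no local failure at 2 years is exp(−2(L+O)) + O × exp(−4L) × (1 − exp(−2(O−L)))/(O−L). At 30% this is 0.442 + 0.435 = 0.877, and at 60% it is 0.144 + 0.710 = 0.854. Failure is then 12.3% and 14.6%, while the censored curve still estimates 9.75%.

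**The case against.** A reader might infer that progression of any kind closes every window and that later failures are never counted. No section says so, and there are good arguments against it.

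- Section 7.3.3 defines local control by progression in or at the PTV, citing section 7.3.1, before it uses the bare word. That progression is the natural antecedent, and a new nodule is progression under section 7.3.2, which section 7.3.3 does not cite. Section 7.3.4 likewise describes its own event first.
- Sections 6.5 and 6.8 schedule the later scans, and section 4.7 is permissive.
- A cell shared by endpoints 1 to 4 would, read literally, also stop counting transplants after progression, yet section 3.1 records transplantation for each participant.

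A reader might also infer that the example participant is scored as locally controlled and that local failure is therefore understated. Section 9.2.3 does not support that: Kaplan-Meier censors at the nodule.

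These points rule out the strong reading. They do not settle the text. The participant-level stops in the synopsis and section 4.7 cannot be read as each endpoint's own event, and nothing says that progression elsewhere leaves a window open. Scheduled scans supply the data but do not tell the analyst whether a later event counts.

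**Conclusion.** The finding holds as an undefined stop event that conflicts with the plan's own follow-up sections. Followed literally, it can end observation before a later PTV failure or metastasis.

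The extrahepatic endpoint is the more exposed, because it is worded as an incidence and has no time-to-event method. The understatement is about 24 to 44% of events under the assumed independent rates, less than one expected event in 15 participants. It reaches about 1.2 events only in the most extreme correlated case shown. Local control loses information, with bias only if sites are correlated. On a site-specific reading both losses are zero.

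Every rate except death is an assumption, and the shared window rests on an extracted table. In a pilot with no formal hypothesis test this should be corrected, but it does not undermine the design.

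**What to change.** 1. In sections 3.2.2, 7.3.3 and 7.3.4, end each window at progression of the type named in that row, transplantation, death or 2 years, whichever is first. For local control that is progression in or at the PTV; for the intrahepatic endpoint, any progression in the liver; for the extrahepatic endpoint, progression outside the liver. Sections 7.3.3 and 7.3.4 currently omit death.
2. State that progression at another site does not end observation for the remaining endpoints.
3. Reconcile the synopsis follow-up and section 4.7 with sections 6.5 and 6.8, so that scheduled scans after other-site progression are used.
4. While section 9.2.3 is open, name the estimator for the extrahepatic endpoint and say how transplantation and death enter it.

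The cost is an amendment to wording, since sections 6.5 and 6.8 already schedule the scans. The downside is that reported failure rates may be slightly less favorable.
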